## **Patient benefit index**

Not applicable

## **Secondary endpoints analysis**

Incidence rate of Fabry associated clinical events will be evaluated as events per 1000 patient – years

If data allows incidence and prevalence will be analyzed in subgroups (i.e., classic males, females, late-onset males, and females)

Renal, cerebrovascular, and cardiac function analyses will be performed in the same subgroups, as well as safety analyses per subgroup.

## **Quality control**

### **Monitoring**

### **Investigator training**

Documents to perform the study will be mailed to physicians who agreed to participate, including the investigator agreements (fees agreement and confidentiality agreement).

Investigators and other designated site staff who have agreed to participate will be trained about the protocol, study procedures and CRF completion by teleconference or on-site visits.

Study variables will be recorded in a CRF, and patient data will be handled preserving confidentiality. Investigators, or other designated site staff will analyze all Fabry patients with amenable mutations and will extract clinical and laboratory features from original medical records (primary source).

## **Audits**

Not applicable

## **Inspections**

Not applicable

### ***Limitations of the research methodology***

The participating center has been selected as the Danish national Fabry center, with more than 20 years of experience managing patients with Fabry disease.

As the clinical data will be collected retrospectively, it is expected that some clinical data will be missing.

## **Protection of human subjects**

### **Ethics and Good Clinical Practice**

The study will be conducted in accordance with ICH GCP. All applicable subject privacy requirements, and the ethical principles that are outlined in the Declaration of Helsinki 2013, including, but not limited to: Danish legal and health authorities and Ethical committee's review and favourable approval of study protocol and any subsequent amendments. The study will be reviewed and approved by the Danish Data Protection Agency, and the Danish Health Data Authority. With special regards to enrolment of patients who is dead, the study will be reviewed and approved by the Scientific Ethics Committee, The Capital Region, Denmark according to the specific legal requirements. Data will be anonymized (coded) when entered in the database.

### **Regulatory framework of the study**

No drug will be evaluated prospectively, therefore, regulatory submission to the Danish Medical Association is not required in Denmark. Regarding data-collection, approval will be acquired from the legal regulatory authorities of the Capital Region of Denmark (see above).

### **Independent Ethics Committee / Institutional Review Board**

No other Institute Review Board.

### **Subject information and consent**

All patients will have provided written informed consent. The Study Team must maintain the original, signed Informed Consent/Accent Form. A copy of the signed Informed Consent/Accent Form must be given to the patient and/or their legally authorized representative.

A dated entry will be available in the patient's chart to confirm that informed consent/assent was obtained prior to any extraction of data and that the patient or their legally authorized representative received a copy of the signed informed consent/assent.

### **Subjects and data confidentiality**

#### **Subject Confidentiality**

Information on patients' identity shall be considered as confidential for all effects and purposes. The patients' identity should not be revealed nor published under any circumstances. Patient data recorded in the CRF will be documented anonymously, coded with a patient number in such a way that only the investigator and site staff may associate data with an identified or identifiable

individual or his/her medical record. All other parties involved in data management, analysis and storage will receive, and subsequently analyze, non-identifiable patient data.

## **Data Confidentiality**

By signing the investigator's confidentiality agreement, the investigator affirms to Amicus that information furnished by Amicus to the investigator will be kept in confidence and such information will be divulged to any expert committee, affiliated institution, and employees only under an appropriate understanding of confidentiality with such committee, affiliated institution, and employees.

## ***Data handling and record keeping***

By signing the investigator's confidentiality agreement, the investigator agrees that, within local regulatory restrictions and ethical considerations, Amicus or any Regulatory Agency may consult and/or copy study documents to verify the included data.

## **Record keeping and archiving**

According to Danish law and to Amicus policies.

The investigator will keep a separate log of subjects' unique identification numbers in a tracker.

Only authorized persons will have access to identifiable personal details, if required for data verification. Data protection and privacy regulations will be observed in capturing, forwarding, processing, and storing subject data. If applicable, subjects will be informed accordingly and will be requested to give their consent on data handling procedures in accordance with national regulations.

In any presentations or in publications of the results of the study, the patients' identities will remain anonymous and confidential. Investigators, or investigator partners defined in annex 1 if applicable and various government health agencies may inspect the records of the study. Every effort will be made to keep the patients' personal medical data confidential.

During the development and analysis of the study, statistical program codes will be locally stored as documents according to best practices. Data protection laws in Denmark will be adhered to at all times. Further, the log file produced during the final run of each program will be stored locally at the investigator site as accompanying documents along with the results.

## **Transfer of Essential Documents**

Not applicable

## **Financing and insurance**

### **Financing**

Senior researchers 2x50% data management 700,000 DKK

Specialist nurse to extract patient data 390,000 DKK

2 Medical students to extract data and manage data files 240,000 DKK

Meetings, IT access, literature review, publication costs 70,000 DKK

**Total 1,400,000 DKK**

Amicus sponsored

**Insurance**

Not applicable

**Management and reporting of adverse events/adverse reactions**

***Adverse event (AE)***

Collection of adverse events as Individual Case Safety Reports (ICSRs) is not required from such retrospective analyses of patient medical records as it is secondary data.

**Plans for disseminating and communicating study results**

The study, and study results, will be disclosed on clinicaltrials.gov and other relevant clinical study disclosure websites in accordance with relevant AMICUS policies. The primary publication is expected to be in an internationally recognised journal, with the Scientific Committee forming the majority of the authorship. Thereafter, any secondary publications will reference the original publication and will be authored in accordance with International Committee of Medical Journal Editors (ICMJE) requirements.

Where required by applicable regulatory requirements, an investigator signatory will be identified for the approval of the clinical study report. The investigator is encouraged to share the summary results with the study subjects, as appropriate.

## Annex 1. List of stand-alone documents

*Documents listed in Annex 1 can be maintained separately from the study protocol. They should be clearly identifiable and provided on request. Write "None" if there is no document or list documents in a table as indicated below.*

Number	Date	Section of study protocol	Amendment or update	Reason
1	xx.xx.2023	Text	Update	Description of participating clinical scientists and research staff

## Annex 2. ENCePP checklist for study protocols

*A copy of the ENCePP Checklist for Study protocols available at [http://www.encepp.eu/standards\\_and\\_guidances/index.html](http://www.encepp.eu/standards_and_guidances/index.html) completed and signed by the main author of the study protocol should be included in Annex 2.*

*The checklist will facilitate the review of the protocol and evaluation of whether investigators have considered important methodological aspects.*

*In question 9.5 of the Checklist, Revision 1:*

*"Study start" means "Start of data collection"*

*"Study progress" means "Progress report(s)"*

*"Study completion" means "End of data collection"*

*"Reporting" means "Final report of the study results"*

## Annex 3. Additional information

*Additional annexes may be included if necessary.*

FACE	Fabry-associated clinical event
FEV1	Forced exploratory volume after 1 second
FVC	Forced vital capacity
LVEF	left ventricular ejection fraction
LVMi	Left ventricular mass index
lyso-Gb ₃	globotriaosylsphingosine
MCS	SF-36 Health Questionnaire Mental Component Score
MedDRA [®]	Medical Dictionary for Regulatory Activities
MMRM	mixed model for repeated measures
MRI	Magnetic resonance imaging
MWFS	mid-wall fractional shortening
NHP	Nottingham Health Profile
NT-proBNP	N-terminal pro b-type natriuretic peptide
PCS	SF-36 Health Questionnaire Physical Component Score
PRO	patient reported outcomes
SAE	serious adverse event
SAP	Statistical Analysis Plan
UA/NSTEMI	non-ST segment elevation myocardial infarction
UPCR	Urine Protein to Creatinine Ratio

Abbreviation	Definition of Term
WBC	White blood cell
WHO-DRUG	World Health Organization Drug Dictionary

1. INTRODUCTION

This document outlines the statistical methods to be implemented during the analyses of data collected within the scope of Amicus Therapeutics Protocol Number: EC22-008 “A Real World Evidence Study of Danish Fabry patients: a > 20-year Longitudinal Retrospective Analysis of Prospectively Collected Data”, version 2 dated 24 October 2023.

The purpose of this SAP is to provide a framework in which answers to the protocol objectives may be achieved in a statistically rigorous fashion, without bias or analytical deficiencies. Specifically, this plan has the following purposes:

- To outline the specific types of analyses and presentations of data prospectively that will form the basis for conclusions.
- To explain in detail how the data will be handled and analyzed, adhering to commonly accepted standards and practices of biostatistical analysis in the pharmaceutical industry. Any deviations from these guidelines must be substantiated by sound statistical reasoning and documented in writing in the final study report.

2. OVERVIEW OF STUDY DESIGN

This is a retrospective study of prospectively collected patient data with the use of secondary patient data from both paper and electronic patient files. All patients are treatment naïve at time of diagnosis. Both migalastat and ERT will be studied retrospectively. Also untreated patients will be studied by assessment of relevant clinical and laboratory variables. The analysis will originate at the time of diagnosis.

The patients have been followed for more than 20 years from 2001 until December 2023. All identified patients with Fabry disease, whether receiving specific Fabry medication or not, have been offered annual or biannual thorough workups including examinations of Fabry associated organ function and symptoms. The study will be carried out at the Danish National Fabry Centre, Department of Endocrinology, Copenhagen University Hospital.

All patients from the Danish National Fabry Centre will be included. Subgrouping is aimed at depending on available numbers: non-amenable, amenable, classic, non-classic, males, females, treated including type of treatment or untreated.

2.1. Study Objectives

To investigate time to first Fabry associated clinical event (FACE) (cardiac, renal, cerebrovascular, including death due to FACE) with particular focus on migalastat clinical outcomes and treatment outcomes preceding migalastat therapy.

To investigate the incidence and prevalence of FACEs with respect to Fabry specific treatment, (migalastat, ERT) or no treatment.

To describe FACEs in accordance with different genotypic and phenotypic groups.

2.1.1. Primary objectives

To investigate Fabry associated clinical events (cardiac, renal and cerebrovascular) with particular focus on migalastat clinical outcomes from the start of treatment and treatment outcomes preceding migalastat therapy.

Details will be provided in the effectiveness analysis.

2.1.2. Secondary objectives

To investigate the incidence and prevalence of FACEs with respect to each cohort: migalastat, ERT, or no treatment.

To describe FACEs in accordance with different genotypic and phenotypic groups.

To investigate the incidence and time to a first fatal or non-fatal cardiac, renal, and cerebrovascular clinical event, separated by each category.

2.1.3. Exploratory objectives

To describe disease progression with focus on organ involvement.

3. STUDY ENDPOINTS

3.1. Primary Effectiveness Analysis

The primary endpoint is time to first FACE (cardiac, renal, or cerebrovascular events) ") since start of treatment for migalastat and or ERT and from time of diagnosis for untreated with particular focus on the added value of the recent addition of migalastat as a treatment option. A formal statistical analysis will be using the initial treatment cohort. Descriptive statistics will be calculated since each start of treatment (after each switch).

FACEs are defined as the following:

- Cardiac clinical events:
 - Myocardial infarction
 - New symptomatic arrhythmia requiring medication, direct current cardioversion, or interventional procedure (e.g., ablation, pacemaker, or defibrillator implantation)
 - Unstable angina defined by national practice guidelines and accompanied by electrocardiographic changes and non-ST segment elevation myocardial infarction [UA/NSTEMI]) and accompanied by electrocardiographic changes
 - Congestive heart failure requiring hospitalization
 - Any major cardiac medical procedure (e.g., valve replacement, stent-implantation, transplant, or persistent atrial fibrillation)
- Cerebrovascular clinical events:
 - Stroke (documented by a physician)
 - Transient ischemic attack (documented by a physician)
- Renal clinical events
 - Doubling of serum creatinine level from the start of analysis (2 consecutive values)
 - End-stage renal disease (ESRD) requiring long-term dialysis or transplantation
- Death due to FACEs

All FACEs will be analyzed together as a composite and separately in each category (cardiac, cerebrovascular, and renal). Death due to FACE will be analyzed under the category in which it occurred (cardiac, cerebrovascular, or renal).

3.2. Secondary Effectiveness Analysis

Secondary endpoints listed below will be assessed by evaluating migalastat-treated and untreated patients and/or migalastat-treated and ERT-treated patients:

- The prevalence of FACEs from each baseline (diagnosis, and start of treatment) in migalastat-treated, ERT-treated patients and untreated patients

- The incidence of FACEs from each baseline (diagnosis, and start of treatment in migalastat-treated, ERT-treated patients and untreated patients
- Time to the first cardiac, cerebrovascular, and renal clinical event separately by each specific category (including death in these categories) from baseline (diagnosis and start of each treatment) using Cox proportional hazards model and descriptive statistics.
- Incidence of cardiac, cerebrovascular, and renal clinical events separately by each specific category (including death in these categories)
- Occurrence of cardiac, cerebrovascular, and renal clinical events separately by each specific category (including death in these categories)
- Annualized rate of change in eGFR based on the Chronic Kidney Disease Epidemiology Collaboration equation (eGFR CKD-EPI) over time in migalastat-treated, ERT, and untreated patients . Analysis will also be performed by eGFR category at baseline if the counts are sufficient.
- The prevalence and incidence of a clinically significant change in mGFR and/or eGFR (according to KDIGO guidelines rapid progression is defined as a sustained decline in eGFR of more than 5 ml/min/1.73 m²/yr) from each baseline (diagnosis, and start of treatment) in migalastat-treated, ERT-treated patients and untreated patients.
- The prevalence and incidence of micro (> 30 mg/g creatinine) or macroalbuminuria (> 300) by urinary albumin/creatinine ratio (ACR) or urinary 24 h protein excretion from each baseline (diagnosis, and start of treatment) in migalastat-treated, ERT-treated patients and untreated patients.

The analysis for the primary effectiveness endpoint will be performed at the 2-sided significance level of 0.05 to compare migalastat-treated and untreated patients. All other comparisons will also be done at the 2-sided significance level of 0.05 with no adjustment for multiple comparisons.

3.2.1. Pharmacodynamic Endpoints

Pharmacodynamic endpoints will be assessed by evaluations comparing migalastat-treated and untreated patients and/or migalastat-treated and ERT-treated patients:

- Plasma lyso-Gb₃
- WBC α -Gal A enzyme activity in males
- Leukocyte and plasma Gb3, lyso-Gb3, and α -GAL A enzyme activity
- Neutralizing antibodies during the ERT treatment

3.2.2. Safety Endpoints

The design of the study is characterised by secondary use of data previously collected from healthcare professionals for other purposes.

For this study, the submission of suspected adverse reactions in the form of ICSRs is therefore not required.

All adverse events/reactions collected for the study should be recorded and summarised in the interim safety analysis and in the final study report unless the protocol provides for different reporting with a due justification.

SAEs

- Vital signs:
 - resting systolic blood pressure
 - resting diastolic blood pressure
- Body weight
- Overall survival among all patients enrolled, as assessed by recorded patient deaths from any cause
- Laboratory parameters:
 - serum creatinine
 - urine creatinine
 - urine protein
 - urine albumin
 - urine ACR
- ECGs
- ECHOs, including left ventricular mass index (LVMi), if medically indicated and requested by a physician
- Occurrence of male infertility
- Infusion related reactions

3.2.3. Exploratory Organ Specific Endpoints

Reflecting the programme of the annual clinical examinations and questionnaires of the Danish Fabry patients.

Lung capacity: clinically significant changes in spirometry measures of obstructive and restrictive lung function evaluated by body plethysmography.

- Forced expiratory volume after 1 second (FEV1)

A clinically relevant change is defined as 25% decrease from baseline or as incident volume of 20% below predicted value according to an age- and sex-adjusted reference range.

- Forced vital capacity (FVC)

A clinically relevant change is defined as 25% decrease from baseline or as incident volume of 20% below predicted value according to an age- and sex-adjusted reference range.

Central and peripheral neurological, assessments

- Standardized sweat test (hypo, normo, hyperhidrosis), standard unit of measure: mg pr. 30 minutes
- Autonomic nerve function (small fibre assessment))
- Presence of Fabry associated abnormalities by brain MRI

Standardized tilt-test (Presence of orthostatism – yes/no)

- Heart rate variability (Age-dependent – impaired vs not)
- Orthostatic blood pressure

Audiological assessments

- Audiogram (Impaired vs not)

Ophthalmological and dermatological assessments

- Presence of cornea verticillata
- Presence of angiokeratoma

Composite phenotypic score

- Mainz Severity Score Index (Composite score)

Cardiac function (evaluated by echocardiography)

- Left ventricular mass index (LVMi)
- Left ventricular ejection fraction (LVEF)
- Fractional shortening
- Left ventricular end diastolic and systolic volumes
- Mid-wall fractional shortening (MWFS)

- Left ventricular wall thickness
- NT-proBNP and high sensitive Troponin T – will be analysed from the Danish Fabry biobank.
- Global longitudinal strain if available

Renal function

- Laboratory parameters: measured glomerular filtration rate by ^{99}Tc -DTPA or ^{51}Cr -EDTA

Other renal function parameters are analyses under effectiveness.

Patient reported outcomes (PRO)

- SF-36 Health Questionnaire (Composite score)
- SF-36 Health Questionnaire Physical Component Score (PCS)
- SF-36 Health Questionnaire Mental Component Score (MCS)
- NHP-Health Profile (Daily living questionnaire – composite score)
- Major Depression Inventory (Composite score)

4. SAMPLE SIZE JUSTIFICATION

Approximately 115 patients with established Fabry Disease, estimated 2/3 female and 1/3 male.

Sample size was not determined statistically. All patients from Danish National Fabry Centre are included.

4.1. Randomization

Not applicable for this study.

4.2. Unblinding Plan

This is a retrospective, multicenter, observational study. No unblinding is necessary.

5. DEFINITION OF PATIENT POPULATIONS TO BE ANALYZED

5.1. Safety Population

The Safety Population will include all patients with Fabry disease who consented to participate and enrolled in the study. Patient disposition and reason for discontinuations will be presented in the Safety Population.

Patients who enter the study as untreated but switch to a treatment (migalastat or ERT) within 3 months from enrollment will be considered in analysis as initially belonging to a treatment group they switched to. Depending on an analysis as further discussed the group assignment might change in the case of a treatment switch.

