## Milestones

Milestone	
Ethics Committee Approval	Q3 2023
Start of data collection	Q3 2023
End of data collection	Q1 2024
Study progress report	Q1 2024
Interim report (baseline data)	Q2 2024
Registration in the EU PAS register	Q3-4 2023
Final report of study results	Q3 2024

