## **Research methods**

### **Study design**

Observational, retrospective, single-center study originating from the Danish National Fabry Centre, Centre of Cancer and Organ Disease, Department of Medical Endocrinology, Copenhagen University Hospital, Rigshospitalet. Patients are enrolled at the time of sampling leading to a genetically verified diagnosis of Fabry disease. Patients are followed from the day of enrolment until 31st of December 2022, having received yearly or bi-yearly evaluation during follow-up.

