## Study workflow

Fabry patients entered the study at their baseline visit (first visit in the center) from 2001 with last follow-up December 2022. Patient data will be grouped for the whole duration of the defined study period, with individual datapoints registered at the specific date of event/measurement. Ideally the datapoints will be used according to their specific dates but may be aggregated according to availability. Details is further described in the statistical analysis plan.

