15.4. Overall Survival

To assess the overall survival among all patients, a Cox proportional hazards model will be used, provided that the assumptions of Cox proportional hazard are met. The ratio of the hazards of treatment groups will be checked to ensure that the hazard ratios are constant over time. Secondly, the assumption that each variable in the model makes a linear contribution will be checked. Otherwise, Kaplan-Meier log-rank test will be used for this analysis.

Overall survival is defined as time from enrollment into the study until death due to any cause (event).

Covariates will include:

- sex
- enrollment age as a continuous variable
- enrollment eGFR as a continuous variable
- LVMi at enrollment
- time on treatment (ERT or migalastat overall)
- history of cardiac, cerebrovascular, and renal clinical events (a binary endpoint based on the composite event) prior to enrollment
- length of therapy for Fabry disease

If the measurements are not available, measurements prior to and closest to the Analysis Start Date will be used. In case that more than 50% of values are missing for a given covariate, it will be dropped from the analysis.

In the Safety Population where patients are analyzed based on the actual exposure, a Cox model run similarly to the analysis in Section [13.1.2](#) will be used but with 3 time-dependent variables indicating whether or not a patient is on migalastat, ERT, or untreated at time t. A patient may be in 1 or more treatment groups and a patient may be both left and right censored. For example, a patient that begins migalastat, stops at Month 3, begins ERT at Month 6, and then dies at Month 9 will be represented 3 times in the design matrix; the first for migalastat being right censored at Month 3, the second being for ERT left censored at Month 3 and right censored at Month 6, and finally, for untreated, being right censored at Month 6 and having an event at Month 9.

The estimate of hazard ratio for migalastat/ERT and migalastat/untreated along with the associated 95% CI will be calculated.

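### SAP 5.1 makes consent a condition of the Safety Population with no exception for deceased patients, whom the Protocol plans to enrol; applied literally, it would bias overall survival upward

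*SAP*

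**What the plan says.** SAP 5.1 defines the population used for every safety summary (SAP 15): "The Safety Population will include all patients with Fabry disease who consented to participate and enrolled in the study". The Protocol, under Subject information and consent, is just as general: "All patients will have provided written informed consent". It also asks for a dated chart entry showing that "informed consent/assent was obtained prior to any extraction of data". Neither text mentions patients who have died.

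The Protocol's section on Ethics and Good Clinical Practice does mention them: "With special regards to enrolment of patients who is dead, the study will be reviewed and approved by the Scientific Ethics Committee". So their enrolment is foreseen, by a route other than their own consent.

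The SAP expects complete coverage. Section 4 includes every patient of the national centre. Section 3.2.2 lists survival among all enrolled patients, based on recorded deaths from any cause. Section 15.4 says "Overall survival is defined as time from enrollment into the study until death due to any cause (event", and section 11.1 sets enrollment at the date of diagnosis, not the date of consent.

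On timing, the Protocol's Milestones give "Start of data collection Q3 2023", with ethics approval in the same quarter. Its Study workflow describes entry from 2001 "with last follow-up December 2022". SAP 2 instead has follow-up running to December 2023.

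**The concern.** A programmer who builds the Safety Population flag from SAP 5.1 alone will leave out any patient without a consent record. If consent was sought only once the study was being set up, being in the population requires having survived to that point, which is selection on the outcome being estimated. Because survival is counted from diagnosis, the whole stretch from diagnosis to consent would be death-free by definition for patients admitted this way, and the SAP has no delayed-entry rule to allow for it.

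The analyses at stake are overall survival (SAP 15.4), the listing of causes of death (SAP 8.2) and fatal SAEs (SAP 15.2). If the general consent sentence in the Protocol is also applied to the effectiveness populations, the FACE deaths in the primary composite and the separate FACE-death analysis (SAP 13.1) are affected, as are the non-fatal FACEs of patients who later died. If it is not applied there, FACE deaths and all-cause deaths will be counted in different sets of patients.

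The loss need not be even across treatments. The Protocol dates migalastat's availability from 2016, so earlier deaths fall on untreated or ERT time, apart from any trial use before approval, which the documents do not describe for this cohort.

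**Working it through.** The plan states no event count, survival rate or power, so there is no figure to reproduce. The check has two parts.

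**1. Do the texts agree on whether a deceased patient is in?**

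| Place | Deceased patient who never consented |
|---|---|
| SAP 5.1 | Out |
| Protocol, Subject information and consent | Out (consent asked of all) |
| Protocol, Ethics and Good Clinical Practice | In, subject to ethics committee approval |
| SAP 4 and 3.2.2 | In (all centre patients; all enrolled) |
| SAP 5.2.1 and 5.2.2 | No consent condition stated |

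They do not agree, and this does not depend on when consent was taken.

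**2. How much could it matter?**

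Inputs:
- N = 115 patients (SAP 4), taken here to include those who have since died.
- D = number of deaths in follow-up. Not given; assumed 5 to 30.
- f = fraction of deceased patients who enter the Safety Population. Not given; 0, 0.5 and 1 are shown.

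Crude survival = 1 − fD / (N − D + fD).

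| D (assumed) | f = 1 | f = 0.5 | f = 0 |
|---|---|---|---|
| 5 | 110/115 = 95.7% | not shown | 110/110 = 100% |
| 10 | 105/115 = 91.3% | 105/110 = 95.5% | 105/105 = 100% |
| 20 | 95/115 = 82.6% | 95/105 = 90.5% | 95/95 = 100% |
| 30 | 85/115 = 73.9% | 85/100 = 85.0% | 85/85 = 100% |

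The f = 0 column needs three conditions together: consent was first taken around Q3 2023, it was required of every patient, and the ethics route adds nobody to the Safety Population. With the Protocol's cut-off of December 2022, every death in the window then precedes consent.

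Under the SAP's cut-off of December 2023 the same three conditions leave a short period after consent, about 0.25 to 0.5 year. That is at most 0.5/23 = 2% of a 2001–2023 window. At assumed death rates of 0.5% to 3% a year:

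- lowest: 115 × 0.005 × 0.25 = 0.14 expected deaths, survival 99.9%
- highest: 115 × 0.03 × 0.5 = 1.7 expected deaths, survival 98.5%

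With none or very few deaths, the hazard ratios planned in SAP 15.4 could not usefully be estimated.

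**The case against.** A reader might infer that patients who died are excluded and that overall survival is about 100% by construction. The documents do not support that, for these reasons:

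- The Protocol's ethics section plans the enrolment of deceased patients. If that route is used, survival is not fixed in advance.
- The SAP is written as though deaths will be seen. The worked example in 15.4 is a patient who dies, 15.2 has a fatal outcome category, and 8.2 lists the primary cause of death.
- No text dates consent. It must precede extraction, so Q3 2023 is when extraction may begin, not when consent was given. Earlier consent at the centre cannot be ruled out, and the consent section mentions legally authorised representatives.
- Under the SAP's own cut-off, follow-up had not closed when data collection began.
- The effectiveness populations carry no consent condition of their own, and neither do the Protocol's inclusion and exclusion criteria.
- The SAP cites Protocol version 2 of 24 October 2023, while the Protocol available is labelled V1. Whether version 2 changed these sections cannot be checked.

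All of this stands, and it makes the size of any bias conditional. It does not remove the contradiction. The ethics provision is not carried into any SAP population definition, and SAP 5.1 is the text from which the population will be built. Intent stated in one document does not correct an operative rule in the other. Inclusion of only some of the deceased also biases the result.

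**Conclusion.** The point holds as a contradiction that must be settled before the populations are fixed. SAP 5.1 and the Protocol's consent section, read literally, leave out deceased patients who never consented; the Protocol's ethics section and SAP 4 and 3.2.2 count them in.

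If the literal rule is followed and consent was first sought around Q3 2023, overall survival from diagnosis is biased upward. For an assumed 10 deaths in 115, the overstatement is 8.7 percentage points if no deceased patient enters (100 − 91.3) and about 4.2 if half do (95.5 − 91.3). For 20 deaths it is 17.4 and 7.9 points (100 − 82.6; 90.5 − 82.6). The number of deaths, the consent dates and the uptake of the ethics route are all unknown, so these are illustrations and not estimates. The effect on the primary composite is less certain, because it arises only through the Protocol's general consent sentence.

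**What to change.** 1. In SAP 5.1, define the Safety Population as patients who consented, or who are included under the ethics committee approval for deceased patients.
2. In the Protocol's consent section, limit the written-consent requirement to living patients and cross-refer to the ethics section for those who have died.
3. State in SAP 5.2.1 and 5.2.2 that the same rule applies to both effectiveness populations, so that FACE deaths and all-cause deaths come from one cohort.
4. Add to SAP 8.1 a table of patients registered at the centre since 2001: consented, deceased and included, and not included, with reasons. Show deaths among those not included where this may be reported.
5. Reconcile the December 2022 and December 2023 ends of follow-up and state one date in both documents.

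The cost is a few sentences, one table and the extraction of the deceased patients' charts. The ethics review is already planned. If it does not permit their inclusion, the report should say that the survival figures describe only patients who were able to consent.
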